Study 2: Our clinical study is a longitudinal randomized (6 month) cross over controlled clinical trial (RCT) intervention with two parallel arms (ratio: 1:1) with care-as-usual plus care coordination intervention. The purpose of Phase-II clinical trial is to examine effectiveness of the Care4AD platform to improve care coordination and caregivers burden and stress. For the purpose of this study, we will recruit 100 men and women older adults (Age 18+) persons with mild or moderate dementia/memory loss. Including self-reported memory loss and MOCA score of 26 or lower.

Both groups will receive identical Care4AD platform (tablet). However, all feedbacks (e.g., reminder about completed/incomplete tasks) will be activated in the intervention group (IG) and the caregiver will have companion app downloaded on their smartphone. Reminder notifications will be de-activated in the control group (CG) and no app will be supplied. CG will receive conventional care coordination intervention through bi-weekly interview and will be provided with

7/25/24, 1:58 PM Human Protocol Report
scheduled care tasks similar to IG. Participants will be informed that the purpose of this program is to examine effectiveness of a care coordination program to reduce stress and burden of care givers and improve adherence to scheduled care tasks and improve mobility. The type of intervention will not be disclosed to participants at baseline (blinded study design) as both groups will receive some sort of care coordination intervention. In addition, the person who will analyze the data will be blinded to the type of intervention. At the 3 month visit, participants will be crossed over to either intervention or control and follow procedures.

Inclusion Criteria:

Male and female older patients (> 18 years old) with mild or moderate memory loss, self- reported memory loss, or MOCA score 26 or lower, and who are ambulatory and are in a residential home with a caregiver/informant or in a nursing home.

Caregivers and Health Professionals will be included in the subject population.

Exclusion Criteria:

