At the 3 month visit, the following procedures will be completed: Questionnaires, Gait, Balance, Motor-Cognitive Exercise program, Spontaneous physical activity monitoring, Upper Extremity Test, Photos and Media. Crossover will also happen, intervention group will become controls and controls will become part of the intervention group.

At 6 months, the following procedures will be completed: Questionnaires, Gait, Balance, Spontaneous physical activity monitoring, Upper Extremity Test, Photos and Media. At the end of the visit, the subject will return the platform to the research team.

Section G: Sample Size/Data Analysis

G1. Sample Size

How many subjects (or specimens, or charts) will be used in this study?

Local: 130 Worldwide: 130

Please indicate why you chose the sample size proposed:

Phase I: N=30 total subjects including 10 eligible Individuals With Dementia, at least one of the caregivers (n=10), and 10 expert clinicians unaffiliated with this project, who are providing care for Individuals With Dementia and their caregivers. The sample size for Phase I is chosen based on our experience with assessing technologies for older populations and also considering the timeline and budget limitation for Phase I. Over the past decade, we have evaluated the usability of a number of such technologies and we have found that the proposed sample size is adequate for identifying potential shortcomings that might require design or implementation modifications.

Phase II: N=100 total subjects, Individuals With care-givers, age 18+, who are supporting an individual with memory loss, aged 50+, male and female, who satisfied inclusion and exclusion criteria described in the following. The required sample size for Phase II was calculated based on our primary endpoints: 1) reduce burden for the caregivers in the Intervention group, 2) better adherence in the Intervention group compared to control group, and 3) change in functional performance over 6 month.

G2. Data Analysis

Provide a description of your plan for data analysis. State the types of comparisons you plan (e.g. comparison of means, comparison of proportions, regressions, analysis of variance). Which is the PRIMARY comparison/analysis? How will the analyses proposed relate to the primary purposes of your study?

7/25/24, 1:58 PM Human Protocol Report

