Study 2: Results of the user experience questionnaires will be calculated as median (range) for each Likert-scale question. Unpaired t-tests, Mann-Whitney u-tests, and Chi-square will be used for baseline between groups comparison to verify effectiveness of randomization. Linear mixed models will be used to test the effect of the Care4AD care coordination intervention on caregiver burden/stress at 6 months compared to baseline and between groups. Mixed models that accommodate the longitudinal design, allow for testing differences between groups in patterns over time, as well as at specific time points are consistent with an intention to treat analysis, and are valid for data which are missing at random. Appropriate mixed models (linear for continuous or Generalized Estimating Equations (GEEs) for non-continuous or non-parametric variables) will be used to test the intervention effect for each of the secondary outcomes (depression, cognitive function, QoL, fear of falls, neurotic tendency including fatigue, physical activity, adverse events, missing appointments). Univariate linear regression analyses will be performed to delineate predictive factors of training response for the primary study endpoint (pre- to post- changes in care coordination outcomes). Baseline values include age, gender, BMI, fear of falling, ADL-status, comorbidity, cognitive performance, depression, stage of AD, and baseline motor variables (e.g., balance and gait speed). We will use Spearman correlation coefficient to compare changes in quantitative metrics of exercise performance over the course of the program with in clinic assessments of functional performance (e.g., gait speed) and cognitive performance (e.g., MoCA). We will assess the agreement between Care4AD derived ADL, the Katz Index, and the Lawton-ADL. To demonstrate the acceptability of Care4AD application, we will use TAM model described above using 5-point Likert response questions. For all assessments, a p-value of 0.050 or less will be considered as statistically significant level. To evaluate the effect of sex as biological variable, we will examine whether acceptability and benefits of Care4AD platform to improve care coordination outcomes (between groups as well as compared to baseline) are different between men and women.

Section H: Potential Risks/Discomforts

H1. Potential Risks/Discomforts

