H3. Coordination of information among sites for multi-site research

Is the BCM Principal Investigator acting as the SPONSOR-INVESTIGATOR for this multi-site research?

No or Not Applicable

Is BCM the COORDINATING CENTER for this multi-site research?

Section I: Potential Benefits

Describe potential benefit(s) to be gained by the individual subject as a result of participating in the planned work.

The main benefit to subjects is the positive feeling that they will have by participating in a study that will potentially help other people by developing new technology that could improve the care of dementia and older adults and could assist in coordinating care, reducing burden and stress of caregivers, as well as improving safety and autonomy of individuals with dementia. They might eventually directly benefit from this technology if the device became validated and available for clinical use in the future. In addition, during the study all participants will receive care coordination intervention, which have been shown to be effective in reducing stress and burden of caregivers, which showed to be effective in improving balance and mobility in people with dementia. The subjects will be compensated for their time (\$50 for Phase I, and \$100 per month for the Phase II). Except baseline screening, no other visits to the clinic is needed for the intervention group.

Describe potential benefit(s) to society of the planned work.

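### Univariate regressions of pre-to-post change, with no control contrast described, cannot in general separate predictors of response to Care4AD from purely prognostic factors

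*Combined protocol and SAP*

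**What the plan says.** G2. Data Analysis (Study 2) states the method and its purpose: "Univariate linear regression analyses will be performed to delineate predictive factors of training response for the primary study endpoint". The dependent variable is given as "pre- to post- changes in care coordination outcomes". The candidate predictors follow: "Baseline values include age, gender, BMI, fear of falling, ADL-status, comorbidity, cognitive performance, depression, stage of AD, and baseline motor variables", with balance and gait speed as examples of the motor variables.

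The text names no treatment, period or sequence term, no factor-by-treatment interaction, no arm, and no visits for before and after. The significance rule in the same paragraph covers this analysis too: "For all assessments, a p-value of 0.050 or less will be considered as statistically significant level".

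Three statements elsewhere bear on what such a regression would estimate:

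- F1. Design makes the control active: "CG will receive conventional care coordination intervention through bi-weekly interview". Both groups receive the tablet. The intervention adds reminders and a caregiver app.
- Section I: Potential Benefits says that "during the study all participants will receive care coordination intervention, which have been shown to be effective in reducing stress and burden of caregivers".
- F2. Procedure, 3 month visit: "Crossover will also happen, intervention group will become controls and controls will become part of the intervention group".

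**The concern.** A baseline factor can be related to change in two ways. It may be prognostic, so that people with high values change more whatever they receive. Or it may modify the effect, so that they gain more from the reminders and app than from the control programme. Only the second makes it a predictor of response to Care4AD, and only a comparison with control separates the two.

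The distinction matters in this design. The control programme is itself expected to reduce caregiver burden, so change without reminders is likely. After month 3 everyone has had both conditions, so a baseline-to-6-month change mixes them, and at month 6 the intervention-first half is in the control condition.

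At stake is the reported list of who responds. A purely prognostic factor could be declared a significant predictor of response, and a factor that does modify the effect could go unreported.

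**Working it through.** **Inputs.** From the documents: 100 participants (F1. Design; G1. Sample Size), 1:1 allocation, so 50 per sequence; crossover at 3 months; p of 0.05 or less, taken as two-sided. The documents give no effect size, SD, power or dropout, so the sample size cannot be reproduced, and no figure is stated for the predictor analysis. Assumed: standardised factor x, residual SD of change from baseline 1, correlation 0.5 between 3- and 6-month change, no carryover, no dropout.

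**What each slope estimates.** Write the change as p·x + d·A + g·A·x + error, where A is 1 under reminders plus app and 0 under control, p is prognosis and g is modification.

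- Both groups pooled, baseline to month 3: half have A = 1, so the slope is p + g/2. At month 6 the other half have A = 1, so it is again p + g/2.
- Pooled with a group main effect only: still p + g/2, because x is independent of randomised group.
- Intervention-first arm, 0-3 months: p + g.
- Factor-by-group interaction, 0-3 months: g.

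With p = 0.3 and g = 0.3 these are 0.3 + 0.15 = 0.45, 0.45, 0.60 and 0.30.

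**A purely prognostic factor (g = 0).** The pooled slope has a standard error of about 0.101. For p = 0.2, 0.3 and 0.4, p/0.101 is 1.98, 2.97 and 3.96. Against a critical value of 1.985, the chance of being flagged is about 50%, 84% and 98%. Simulation (20,000 trials per setting) gives:

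| Analysis | p = 0.2 | p = 0.3 | p = 0.4 |
|---|---|---|---|
| Pooled, baseline to month 6 | 50% | 84% | 97% |
| Intervention-first arm, 0-3 months | 28% | 54% | 77% |
| Each person's own Care4AD period, month 3 as the start for the control-first half | 17% | 32% | 49% |
| Control-first half, months 3-6, same prognostic slope at both visits | 5% | 5% | 5% |
| Control-first half, months 3-6, half the slope present by month 3 | 11% | 18% | 28% |
| Factor-by-group interaction, 0-3 months | 5% | 5% | 5% |

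**A true modifier that is missed.** Let the slope be -0.2 under control and +0.2 under reminders plus app, so p = -0.2 and g = 0.4. The pooled slope is -0.2 + 0.4/2 = 0. The pooled 0-3 month regression flags the factor about 5% of the time; the interaction flags it about 48% of the time.

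**Power of the interaction, 0-3 months.** The standard error is about 0.205. For g = 0.3, 0.3/0.205 = 1.46, which gives about 30%. For 0.4 and 0.5, power is about 49% and 67%. With 20% lost (assumed) the three figures are 26%, 40% and 58%. For 80% power, g must be about (1.985 + 0.846) × 0.205 = 0.58 SD.

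**Using both periods.** Without carryover, power at g = 0.3 is about 83%. If a fraction c of the modification carries over in the intervention-first half, the within-person contrast has slope g(1 - c) in that half and g in the other, so on average g(1 - c/2). At c = 1 that is 0.15 instead of 0.30. Power falls to about 71%, 58% and 31% at c = 0.25, 0.5 and 1. The 0-3 month interaction is unaffected.

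**The case against.** The best reply is that the target is being inferred. The plan speaks of *training response*, never of response to Care4AD over control. No training is described in Study 2 beyond an unexplained motor-cognitive exercise item at the 3-month visit. If the aim is only to describe who changes, the regression is coherent. This stands, and it is why the point is conditional. A reader might infer that the plan certainly sets out to find who benefits from Care4AD; the documents do not say so. The wording still invites that reading and should be settled.

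Second, the text is brief, *univariate* may mean one outcome, and silence does not exclude a group term. That is true, but a group main effect would leave the slope at p + g/2. Only an interaction isolates g.

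Third, the flagging rates are the power to detect a real association with change, at slopes that the documents do not give. That is correct. They become wrong claims only when reported as response to Care4AD.

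Fourth, one reading escapes: the month 3-to-6 change in the control-first half. It works only if prognosis has the same slope at both visits, and the plan does not specify it.

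A reader might also extend the criticism to the sex analysis, which looks at whether benefits "between groups as well as compared to baseline) are different between men and women". That clause can be read as between-group differences in change, so it does not clearly share the defect. Testing many factors at one threshold is a separate question and does not bear on this point.

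**Conclusion.** The point holds conditionally. If *training response* means response to the reminders and app over the active control, the described regressions generally cannot identify its predictors, because they estimate prognosis plus half or all of the modification. That follows from the algebra and does not depend on the assumed slopes. The size does: with 50 per sequence and slopes of 0.2 to 0.4 SD, a purely prognostic factor is flagged in 50% to 97% of trials pooled at 6 months and in 28% to 77% in the intervention-first arm, against about 5% for the interaction. These figures assume residual SD 1, no carryover and no dropout.

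It would be wrong to infer that the trial's main result is compromised. F1. Design labels the study a pilot, this is a supporting analysis, and the between-group mixed models for caregiver burden are separate from it.

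**What to change.** 1. Define *training response*, and state which visits and arms the change is taken from.
2. If response to Care4AD is meant, test for each listed factor a factor-by-randomised-group interaction on the 0-3 month change, which carryover cannot affect. Report estimates with 95% confidence intervals and label them exploratory.
3. Use a two-period mixed model (factor-by-condition, period, sequence and factor-by-period terms) only as a supporting analysis, because no washout is stated and carryover would attenuate its estimate.
4. If univariate regressions are kept, call the results prognostic associations with change, not predictors of response to Care4AD.

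**Cost.** No new data or visits, and a little analysis work to write the models out. The real price is power: about 30% for a 0.3 SD modification in the 0-3 month comparison with 50 per group, so a null interaction should not be read as evidence that a factor does not matter. Relabelling alone costs nothing and removes the risk of misinterpretation, but leaves the question of who responds unanswered.

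### At least eleven baseline factors are tested one at a time at p ≤ 0.050 as predictors of response, unadjusted and not labelled exploratory: 43% chance of a false predictor if the tests are independent, less if the factors are correlated

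*Combined protocol and SAP*

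**What the plan says.** All of the relevant analysis text is in section G2 (Data Analysis), Study 2.

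- **The analysis.** "Univariate linear regression analyses will be performed to delineate predictive factors of training response for the primary study endpoint". The endpoint is glossed in parentheses as "pre- to post- changes in care coordination outcomes", in the plural.
- **The candidates.** The list is "age, gender, BMI, fear of falling, ADL-status, comorbidity, cognitive performance, depression, stage of AD, and baseline motor variables (e.g., balance and gait speed". Balance and gait speed are given only as examples of motor variables, so the list is open at that end.
- **The decision rule.** "For all assessments, a p-value of 0.050 or less will be considered as statistically significant level". No assessment is exempted.

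G2 does not adjust for the number of factors, does not follow the univariate regressions with a multivariable model, and does not call this analysis exploratory. It states no error rate for the screen and no correlation among the factors.

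Section G1 sets the size of Study 2 ("Phase II: N=100 total subjects") and lists three primary endpoints, starting with "1) reduce burden for the caregivers in the Intervention group, 2) better adherence in the Intervention group compared to control group" and ending with functional performance. G2 does not say which of these the predictor screen uses.

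**The concern.** Each regression taken alone has a 5% chance of a false positive under the stated rule. The output of the screen, however, is a list: the factors said to predict response. What matters for a reader of that list is the chance that it contains at least one false entry, and that chance grows with the number of factors tried. Because G2 places the screen under the same significance rule as every other assessment, a chance finding would be reported in the same terms as a treatment effect.

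A second weakness does not depend on any error rate. Several of the listed factors plausibly overlap: ADL status, cognitive performance, stage of AD, gait speed and balance. Separate regressions cannot distinguish shared from distinct information, so one underlying signal could appear under several names as if there were several predictors.

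What is at stake is the credibility of the predictor list. The comparisons between Care4AD and control do not depend on it.

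**Working it through.** The plan gives no error rate for this screen, so there is no stated figure to reproduce first.

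**Inputs from the documents**
- Per-test level: 0.050 (G2).
- Number of factors: age, gender, BMI, fear of falling, ADL status, comorbidity, cognitive performance, depression and stage of AD make 9. Balance and gait speed make 2 more. Total k = 11, as a minimum.
- Sample size: 100 (G1). It has almost no effect on the result.

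**Assumptions, not in the documents**
- No factor truly predicts the outcome.
- Tests are two-sided (G2 does not say).
- One outcome is screened.
- Where correlation is used, all pairs of factors share the same value ρ.

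**Step 1. Independent tests**

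P(at least one p ≤ 0.05) = 1 − (1 − 0.05)^k = 1 − 0.95^11 = 0.431.

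Expected number of false predictors = 11 × 0.05 = 0.55. This holds at any correlation.

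**Step 2. Correlated factors**

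With no true effect, the test statistics are correlated about as strongly as the factors. Write each statistic as Z_i = √ρ·U + √(1 − ρ)·E_i, with U and E_i independent standard normal. Then

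P = 1 − ∫ [Φ((1.96 − √ρ·u)/√(1 − ρ)) − Φ((−1.96 − √ρ·u)/√(1 − ρ))]^11 φ(u) du.

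This was evaluated numerically. It was also checked by simulating the slope t-tests at n = 100 (20,000 trials per setting):

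| Assumed common correlation | Integration | Simulation |
|---|---|---|
| 0 | 43.1% | 43.1% |
| 0.3 | 37.5% | 37.8% |
| 0.5 | 30.4% | 30.8% |
| 0.8 | 18.0% | 17.7% |
| 0.9 | – | 13.2% |

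At n = 50 the simulation gives 43.1%, 38.1%, 30.8% and 18.3% for correlations 0, 0.3, 0.5 and 0.8. These match within simulation error.

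**Step 3. A less uniform structure**

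A single correlation across age, gender, BMI and the clinical scales is a strong assumption. If age, gender and BMI are independent of everything and only the other eight factors share a correlation, the simulated chance is 40% at 0.3, 36% at 0.5, 31% at 0.7 and 28% at 0.8.

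**Step 4. More motor variables**

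The gait and balance systems described in F2 yield many parameters, and G2 leaves the motor list open. With 15 factors the chance is 1 − 0.95^15 = 0.537 if independent. By simulation it is 36% at correlation 0.5 and 20% at 0.8. So 43% is not an upper limit.

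**Step 5. What adjustment does**

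When no factor predicts, any factor named is a false one. Benjamini-Hochberg at 5% then brings the chance of naming at least one to 5% or less in the three cases 0, 0.5 and 0.8. Bonferroni, for comparison, tests each factor at 0.05/11 = 0.0045 and gives 1 − (1 − 0.05/11)^11 = 0.049 under independence.

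**The case against.** The strongest reply is that section F1 classifies the research as a pilot, that finding predictors is not among the objectives in section D, and that no treatment comparison rests on this screen. A reader may say it is plainly exploratory. This limits the seriousness of the point but does not remove it. G2 does not say the screen is exploratory, ties it to the primary endpoint, and applies one significance rule to everything. If exploration is intended, a sentence settles it.

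A second reply is that correlation lowers the rate and the documents give none. That stands: 30% and 18% are illustrations, and neither is a property of this trial. The 43% needs independence, which is also an assumption. Even at a common correlation of 0.9 the chance is 13%.

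Three stronger readings are tempting and are not supported:

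- *That the screen will be run for all three G1 endpoints, with a correspondingly larger error rate.* G2 restricts it to care coordination outcomes without fixing their number, and functional performance is not obviously one of them. Any figure would also need correlations among the outcomes as well as among the factors. Only the direction can be stated: more outcomes, higher rate.
- *That later targeting of Care4AD would rest on the list.* No section says so.
- *That a penalised model would stop overlapping factors from each being named.* Ridge keeps every factor, and lasso may choose arbitrarily within a correlated set.

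A further objection is that the regressions, as described, contain no treatment-by-factor term in a trial whose groups cross over at 3 months. They therefore cannot separate response to Care4AD from change that would have occurred anyway. That is a separate defect. Correcting the multiplicity does not solve it, and it does not excuse the multiplicity.

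**Conclusion.** The point holds. G2 plans at least eleven one-at-a-time tests at p ≤ 0.050 to name predictors, with no adjustment, joint model or exploratory label. If none of the factors predicts, the chance of naming at least one is 43% under independence. Under an assumed common correlation it is about 30% at 0.5 and 18% at 0.8. These figures assume two-sided tests, exactly eleven factors and one outcome. More motor variables or outcomes would raise them.

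Severity is low. The screen is ancillary and the primary and secondary treatment comparisons do not use it. The number of factors and the decision rule come straight from G2. The exact rate is less certain, because it turns on a correlation that the documents do not give.

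**What to change.** In G2, Study 2:

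1. Exempt the predictor screen from the p ≤ 0.050 rule and label it hypothesis-generating.
2. Run it for one named outcome, for example change in caregiver burden, and list the motor variables to be used so that the number of factors is fixed.
3. Report the estimate for every factor with its 95% CI and a Benjamini-Hochberg adjusted p-value (5%), whatever the result.
4. Fit one multivariable model with the listed factors and show each factor's estimate from it beside the univariate estimate, so that overlap between factors is visible.

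The cost is a few sentences in G2 and a little extra analysis of data already being collected, with no new visits, measurements or subjects. The downside is that fewer factors will be called significant.

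### G1 sizes Study 2 on three primary endpoints, but G2 tests only caregiver burden directly, and the one burden contrast it names, at 6 months, falls after the arms have swapped

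*Combined protocol and SAP*

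**What the plan says.** **Basis of the sample size (G1, Phase II).** "The required sample size for Phase II was calculated based on our primary endpoints: 1) reduce burden for the caregivers in the Intervention group", then "2) better adherence in the Intervention group compared to control group, and 3) change in functional performance over 6 month". No effect size, SD, power, correlation or dropout is given.

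**Analysis (G2, Study 2).** The form asks "Which is the PRIMARY comparison/analysis". The answer attaches that label to no analysis. It opens with linear mixed models for "caregiver burden/stress at 6 months compared to baseline and between groups". It adds that mixed models can compare the groups' trajectories and can compare them at individual visits. It then lists "secondary outcomes (depression, cognitive function, QoL, fear of falls, neurotic tendency including fatigue, physical activity, adverse events, missing appointments"). The only thing it calls primary appears in a sentence on predictors of response: "the primary study endpoint (pre- to post- changes in care coordination outcomes"). The same term returns in the analysis by sex, "care coordination outcomes (between groups as well as compared to baseline"), again without a definition. Functional performance enters as baseline predictors and in a Spearman correlation with "in clinic assessments of functional performance (e.g., gait speed").

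**Design (F1 and F2).** Allocation is 1:1, with visits at baseline, 3 months and 6 months. At the 3-month visit each group moves to the other condition. No washout is described.

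**The concern.** Two things do not fit together.

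First, the endpoints said to determine N are not the endpoints that G2 tests. Overall adherence has no intervention comparison; missed appointments, a partial proxy, is a secondary outcome. Gait and balance have none either; physical activity is secondary and is not the same measure. Section D lists care coordination separately from adherence and burden, so the undefined G2 term cannot be taken as a synonym for either.

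Second, the named burden contrast sits at a visit by which both sequences have had both conditions. G1's third endpoint, change over the full 6 months, has the same difficulty.

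F1 categorises the study as a pilot, which lowers the stakes. But F1 also gives the purpose of Phase II as examining effectiveness, and G1 presents a calculated N. As the text stands, endpoint, contrast and period remain open.

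**Working it through.** **1. G1 against G2**

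| G1 primary endpoint | Intervention test in G2 |
|---|---|
| Caregiver burden | Yes: mixed model, 6 months |
| Adherence | None for overall adherence; missed appointments is secondary |
| Functional performance | None for gait or balance; physical activity is secondary |

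One of the three has a direct test.

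**2. Can N=100 be reproduced?** No, because its inputs are absent. Under the usual formula for two means, several input sets give about 100: 0.56 SD at 80% power, two-sided 0.05 (102 in total); 0.65 SD at 90% (100); 0.5 SD at 80%, one-sided 0.05 (100). None can be tied to a particular endpoint.

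**3. What the 6-month contrast estimates.** Let τ be the benefit while on the platform, c the fraction that persists after it is switched off, and let the time trend be equal in both sequences. Relative to that trend, at 6 months:
- the Care4AD-first sequence, now on control, stands at cτ;
- the control-first sequence, now on Care4AD, stands at τ.

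By randomised arm the difference is cτ − τ = −(1−c)τ. By condition in use it is τ − cτ = (1−c)τ. Change from baseline in either sequence combines the time trend with one period on and one period off the platform, so it does not isolate Care4AD.

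**4. Size, under assumptions.** Take τ = 0.566 SD, which has 80% power at 3 months with 50 per arm (two-sample t, 98 df, SE = √(2/50) = 0.2 SD).

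| c | Size of 6-month difference | Chance of significance favouring the sequence then on Care4AD |
|---|---|---|
| 0 | 0.57 SD | 80% |
| 0.5 | 0.28 SD | 29% |
| 1 | 0 | 2.5% |

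Read by current condition, the last column is the chance of showing the benefit. Read by randomised arm, it is the chance of a significant result against the Care4AD-first arm.

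**5. What valid contrasts would detect** (80% power, two-sided 0.05, t-based)

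(a) 3-month difference between arms: SE = SD·√(2/n per arm). Baseline adjustment multiplies it by √(1−ρ²), where ρ is the assumed correlation between baseline and 3 months.

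(b) Two-period model: SE = SD·√((1−ρ)/n per sequence), where ρ is the assumed within-caregiver correlation between periods.

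| Contrast | 50 per sequence | 25 per sequence |
|---|---|---|
| (a) unadjusted | 0.57 SD | 0.81 SD |
| (b) ρ = 0.3 / 0.5 / 0.7 | 0.34 / 0.28 / 0.22 SD | 0.48 / 0.40 / 0.31 SD |

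At 50 per arm, baseline adjustment brings (a) to 0.54, 0.49 or 0.40 SD at ρ = 0.3, 0.5 or 0.7.

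The second column is needed because F1 counts 100 persons with memory loss while G1 describes caregivers. If the 100 includes both members of each pair, there are 100/2/2 = 25 pairs per sequence, and power at 0.566 SD under (a) is 50%.

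Under (b) the expected estimate averages τ and (1−c)τ, that is τ(1−c/2): 75% of the true effect at c = 0.5 and 50% at c = 1. At ρ = 0.5 and a true effect of 0.283 SD, with 50 per sequence, power falls from 80% to 56% or 29%.

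**The case against.** The strongest reply is G2's own description of mixed models, which covers comparisons over time and at single visits. That allows a 3-month contrast and does not exclude coding treatment by period. This stands: a reader might infer that the plan rules out a valid crossover analysis, and it does not. The defect is that G2 names no 3-month contrast, no treatment-by-period coding and no period, sequence or carry-over term, while the one burden contrast it does name is at 6 months.

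A reader might also infer that the 6-month result must come out with the wrong sign. The documents do not support that. F2 describes the intervention group as becoming controls and the reverse, so *groups* at 6 months may mean current condition. The sign is then right and, without carry-over, power equals that at 3 months. The intention-to-treat wording in G2 gives some support to the other reading. The ambiguity is the problem.

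Nor is it fair to say that the plan has no primary outcome. Burden comes first and is absent from the secondary list, so it is primary by implication.

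Finally, F1 blinds the person analysing the data to the type of intervention. This limits selective choice of a contrast but does not replace specifying one.

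**Conclusion.** The concern holds as a mismatch between G1 and G2 together with an unsuitable 6-month burden contrast. It should be fixed, though the pilot category limits its weight. Two of the three endpoints said to set N have no direct intervention test. For the third, the named contrast is reversed or diluted if read by randomised arm, and open to carry-over if read by current condition.

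The mismatch and the expressions ∓(1−c)τ need no assumed effect size; the latter assume only an equal time trend in both sequences. All powers and detectable differences rest on assumed effects, correlations, carry-over fractions and numbers per sequence, because the documents give none of these.

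A reader might infer an inflated false-positive rate from three primary endpoints each judged at 0.05. The documents do not support a figure: two of those tests are not planned, and no rule says that any one success suffices.

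**What to change.** 1. Make G1 and G2 name the same primary endpoint or endpoints. The Zarit Burden Interview is one candidate: it is among the F2 questionnaires, which are repeated at 3 and 6 months.
2. Replace the 6-month contrast with one chosen in advance, at two-sided 0.05: (a) the baseline-adjusted difference between randomised arms at 3 months, or (b) the treatment effect over both periods from a mixed model with treatment, period and sequence terms and a stated carry-over assumption. Make 6 months versus baseline descriptive.
3. Give overall adherence and one pre-named functional measure (gait speed is the plan's own example) a model with the same contrast, as secondary outcomes. If they stay primary, state the success rule: all required, a fixed sequence, or Holm.
4. Define the care coordination outcomes or remove the term.
5. State who the 100 are, and give the inputs behind that number.

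**Cost.** For burden this is a change of wording, with no new data. Option (a) leaves second-period data out of the primary test; option (b) is more precise but depends on the carry-over assumption. Adherence and function either lose primary status or become harder to claim. For adherence, the plan should also say whether the bi-weekly compliance calls in F2 are the same contacts as the control group's bi-weekly interview in F1, since measurement and control condition would then overlap.
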